5.6. Analyses of Efficacy Variables

The primary efficacy analyses for all the efficacy endpoints will be conducted at week 24 using the SAF population. The continuous efficacy variables will be summarized using number of patients, mean, SD, minimum, median, Q1, Q3 and maximum. The categorical efficacy variable will be summarized using patient count and proportion. The analyses of efficacy variables are described in the subsections below and summarized in Section 10.1.

Protocol: R668-ALG-1702

Date: March 3, 2021

5.6.1. Analysis of Primary Efficacy Variable

The primary endpoint will be analyzed using descriptive statistics. Estimate of proportion and the 2-sided 95% Clopper-Pearson confidence interval will be provided. The number and percentage of patients at each dose level for highest tolerated peanut protein dose at week 24 DBPCFC will also be summarized.

Missing data for week 24 DBPCFC will be handled according to the reason for missingness as follows:

- If a patient misses the week 24 DBPCFC due to COVID-19, the missing data will be imputed by multiple imputation (MI) method for 10 times utilizing available week 24 DBPCFC data. The MI will utilize logistic regression method with baseline tolerated cumulative amount of peanut protein DBPCFC.
- If a patient does not have available DBPCFC data at week 24 due to reasons not related to COVID-19, the patient will be considered as a non-responder at week 24.

Each of complete datasets after the above steps will be summarized with estimated proportions and standard errors. The SAS MIANALYZE procedure will be used to generate valid statistical inferences by combining results using Rubin's formula (Rubin, 1987).

Supportive analysis of the primary endpoint will include an analysis of patients who have available week 24 DBPCFC of peanut protein.

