8.3.2. Study Drug Discontinuation

Patients who permanently discontinue from study drug and who do not withdraw from the study will be asked to return to the clinic for all remaining study visits per the visit schedule.

Patients who permanently discontinue from study drug and who opt to withdraw from the study will be asked to complete study assessments, per Section 9.1.2.

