11.4.3.1. Primary Efficacy Analysis

The FAS will be used for the primary efficacy endpoint. The primary endpoint will be analyzed using one-sample Chi-square test. Estimate of proportion, p-value, and the 2-sided 95% confidence interval will be provided.

If a patient does not have available DBPCFC data at week 24, the patient will be considered as a non-responder regardless of reasons for missing data.

Sensitivity analyses of the primary endpoint will include an analysis of the subset of patients with available week 24 DBPCFC. Other sensitivity analyses may be proposed in the SAP.

Subgroup analysis (eg, by baseline weight group) will be performed.

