5.4. Patient Disposition

The following summaries will be provided:

- The total number of screened patients and the screen failure reasons including screen failure at visit 1 and visit 1a
- The total number of enrolled patients
- The total number of patients in each analysis set
- The total number of patients who discontinued the study and the reasons for discontinuation (including COVID-19 related reasons)
- The total number of patients who discontinued the study treatment permanently and the reasons for discontinuation (including COVID-19 related reasons)

The following listings will be provided:

- Listing of patients disposition including: date of enrollment, date of first study drug injection, date of the last visit, completed study or discontinued by reason
- Listing of patients enrolled but not treated, and treated but not enrolled
- Listing of patients prematurely discontinued from the study or study treatment, along with reasons for discontinuation
- A listing of protocol deviations will be provided

Kaplan-Meier curve for time to withdraw from the study and from the study treatment will be created, respectively.

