5.6.2. Analysis of Secondary Efficacy Variables

All secondary endpoints will be analyzed descriptively at given visits. SAF will be used for efficacy analysis at week 24, and subset of SAF at week 36 will be used for efficacy analysis at week 36.

Continuous Endpoint at week 24

The change from baseline to week 24 in the cumulative tolerated dose (log transformed) of peanut protein during a DBPCFC will be summarized descriptively. Estimate of change from baseline to week 24 and the 2-sided 95% confidence interval will be provided. If patients do not tolerate any dose level of peanut protein challenge, they will be assigned a cumulative tolerated dose of 1 mg prior to converting to the log scale.

Missing data for week 24 DBPCFC will be handled according to the reason for missingness as follows:

• If a patient misses the week 24 DBPCFC due to COVID-19, the missing data will be imputed by MI method for 10 times utilizing available week 24 DBPCFC data. The MI will utilize logistic regression method with baseline tolerated cumulative amount of peanut protein DBPCFC.

Protocol: R668-ALG-1702

Date: March 3, 2021

• If a patient does not have an available week 24 DBPCFC due to reasons not related to COVID-19, the baseline value at screening DBPCFC will be used to impute the missing week 24 DBPCFC data.

Each of the complete datasets after the above steps will be summarized with estimated means and standard errors of change from baseline to week 24 in the cumulative tolerated dose (log transformed) of peanut protein. The SAS MIANALYZE procedure will be used to generate valid statistical inferences by combining results.

Supportive analysis will include an analysis of patients who have available week 24 DBPCFC of peanut protein.

Binary Endpoint at week 24

For the below binary endpoints of passing a DBPCFC at week 24, the analysis and imputation methods will be similar to the primary analysis.

- Proportion of patients treated with dupilumab that pass a DBPCFC with at least 1044 mg (cumulative) peanut protein at week 24
- Proportion of patients treated with dupilumab that pass a DBPCFC with at least 2044 mg (cumulative) peanut protein at week 24

Proportion of patients with Grade II or above allergic reactions during the DBPCFC at week 24 will summarized descriptively as well as proportion of patients using ephinephrine as a rescue medication during the DBPCFC at week 24.

Continuous Endpoint at week 36

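### Week 24 challenges missed because of COVID-19 are multiply imputed without regard to treatment status, and no rule takes precedence when the child had already stopped dupilumab for another reason

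*SAP*

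**What the plan says.** SAP 5.6.1 introduces its rules with "Missing data for week 24 DBPCFC will be handled according to the reason for missingness as follows". The first rule is "If a patient misses the week 24 DBPCFC due to COVID-19, the missing data will be imputed by multiple imputation (MI) method", carried out "for 10 times utilizing available week 24 DBPCFC data". The model is given in one sentence: "The MI will utilize logistic regression method with baseline tolerated cumulative amount of peanut protein DBPCFC". The second rule makes a patient whose challenge is missing for any other reason a non-responder. SAP 5.6.2 repeats the split for the log-dose change ("If a patient misses the week 24 DBPCFC due to COVID-19, the missing data will be imputed by MI method"), with the screening value carried into week 24 for other reasons. It handles the 1044 mg and 2044 mg proportions like the primary endpoint.

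Two other places give a different rule for the primary endpoint. Under protocol 11.4.3.1, a patient without week 24 challenge data is handled thus: "the patient will be considered as a non-responder regardless of reasons for missing data". The summary table in SAP 10.1 also lists missing as non-responder for the 444, 1044 and 2044 mg proportions at week 24, and last observation carried forward for the log-dose change. It does not mention multiple imputation (MI). SAP 1.2.3, which lists departures from the protocol, does not mention it either.

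On children who stop the drug, protocol 8.3.2 says: "Patients who permanently discontinue from study drug and who do not withdraw from the study will be asked to return to the clinic". That request covers every visit still to come. The SAP analyses efficacy in everyone who received any dupilumab (3.1).

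**The concern.** Two facts can hold for one child: dupilumab was permanently stopped for a reason unrelated to the pandemic, and the week 24 challenge was then lost to COVID-19. The SAP gives no order of precedence, so the COVID-19 rule applies on its wording. The imputation model has no term for exposure or discontinuation. The child therefore receives roughly the pass probability of the patients who were challenged, most of whom can be expected to have been on treatment. Had the same child missed the visit for a family reason, the result would be non-response, or the baseline value for the log-dose endpoint. The pandemic tells us why the visit was lost. It says nothing about the child's treatment status.

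At stake is a modest upward shift in the primary proportion and in the secondary endpoints that share the rule. The planned supportive analysis would not show it, because it uses only patients with an available week 24 challenge and so leaves these children out.

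**Working it through.** **Inputs.** Planned pass rate 29% and reference rate 8% (protocol 11.2, SAP 2.3); 20 evaluable and 24 enrolled patients (same sections). The number k of affected children is not in the documents. I take 0 to 4 as an assumption, 4 being 24 − 20.

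**The plan's own figure.** One-sample test, normal approximation:

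n = [1.96·√(0.08·0.92) + 0.842·√(0.29·0.71)]² / (0.29 − 0.08)² = 18.9, so 19. The plan states 20, where approximate power is 81.5%. Allowing for 15% dropout, 20/0.85 = 23.5, so 24. The sample size is reproduced closely enough and is not in dispute.

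**Difference between the two rules.** Let q be the pass rate among observed patients, with the other 24 − k patients observed.

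- MI: expected proportion = [(24 − k)q + kq]/24 = q.
- The k children as non-responders: (24 − k)q/24.
- Difference: kq/24.

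| k | q = 8% | q = 29% | q = 50% |
|---|---|---|---|
| 1 | 0.3 points | 1.2 points | 2.1 points |
| 2 | 0.7 | 2.4 | 4.2 |
| 3 | 1.0 | 3.6 | 6.3 |
| 4 | 1.3 | 4.8 | 8.3 |

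A simulation of 10-fold logistic MI with illustrative baseline doses agreed with the 29% and 50% columns to within about 0.4 points.

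**Difference is not bias.** If off-drug children truly pass at rate r, MI is biased by k(q − r)/24 and the non-responder rule by −kr/24. With q = 29% and r = 8%, the bias per child is (0.29 − 0.08)/24 = +0.9 points under MI and −0.08/24 = −0.3 points under the non-responder rule. The full 1.2 points is bias only if r = 0.

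**For scale.** The exact 95% interval for 7/24 is 12.6% to 51.1%.

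**Can the case arise?** The protocol points both ways:

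- Protocol 6.1.3.1 and 8.3.2.1 carry headings under which the listed reasons end both the drug and the food challenge. Both lists include missing two or more consecutive doses. Dosing is every 2 weeks with the last dose at week 22 (6.1), so a child who stops before the week 20 dose misses two. On this reading the challenge is absent for a non-COVID-19 reason and the non-responder rule already applies. What remains is close to a child who missed only the week 22 dose and stopped for an unlisted reason.
- The body of 8.3.2.1 speaks only of stopping study drug dosing. Section 8.3.2 asks off-drug patients to attend all remaining visits. Section 8.7 says that prohibited medication ends treatment but not study participation. Section 6.1 has all patients undergo the week 24 challenge. On this reading any child who stops the drug but stays in the study is still due for week 24.

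**The case against.** The strongest reply is that the gap may be almost empty. If the protocol headings mean what they say, most permanent stops also end the challenge, and the second rule in 5.6.1 already covers them. A reader might infer that any early stop, such as one for an adverse event in the first weeks, would be imputed. The documents do not support that while these sections conflict. This part of the objection stands and limits the reach of the point. It does not remove the point, because other protocol sections say the opposite and the SAP does not say which reading its rule assumes.

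Second, neither document defines stopping dupilumab as failure, and an off-drug child who attends keeps the observed result. Calling the imputed child a treatment failure who is given a completer's chance would go too far: the model draws on all available week 24 challenges, not on completers only. This also stands. The narrower complaint needs no such label. The SAP already counts an off-drug child with a non-COVID-19 miss as a non-responder, and it gives no reason why a COVID-19 miss should change that.

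Third, SAP 10.1 shows no MI. That makes the SAP inconsistent with itself and leaves the programmer to choose; it does not settle the matter in favour of 10.1.

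**Conclusion.** The point holds in a limited form. SAP 5.6.1 and 5.6.2 apply MI to every COVID-19 miss whatever the treatment status, give no precedence for a child already off dupilumab for another reason, and conflict with SAP 10.1 and protocol 11.4.3.1. The effect on the primary proportion is q/24 per affected child: about 1.2 points at the planned 29%, of which about 0.9 is bias if off-drug children pass at 8%. The upward direction assumes that off-drug children pass less often than observed patients, which fits the study hypothesis (protocol 3.1) but is not a figure in the documents.

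Two larger claims are tempting and not supported. A shift of nearly 5 points needs all four children beyond the 20 evaluable to have stopped for a non-COVID-19 reason, stayed in the study, still been due for challenge and missed it because of COVID-19; nothing in the documents suggests this. Nor can one say that the rule decides whether the interval clears 8%. With 6 responders among 20 observed, counting the other four as non-responders gives 6/24, with an exact lower limit of 9.8%, already above 8%. SAP 2.2 still carries the 8% hypothesis, but 1.2.3 removes the p-value, 5.6.1 is descriptive, and no criterion for the interval is stated.

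**What to change.** - In SAP 5.6.1 and 5.6.2, limit MI to patients who had not permanently discontinued dupilumab for a non-COVID-19 reason before the missed challenge. The others are non-responders (5.6.1) or receive the baseline value (5.6.2), whatever the reason for the missed visit. A child who stopped the drug because of COVID-19 stays under MI. SAP 5.4 already plans to report permanent treatment discontinuations with reasons, COVID-19 among them, so no new data are needed.
- Align the SAP 10.1 table with 5.6.1 and 5.6.2, and list the move to MI in 1.2.3.
- Report the protocol's analysis, with all missing week 24 challenges as non-response, as a sensitivity analysis.
- Protocol 6.1.3.1, 8.3.2.1, 8.3.2, 8.7 and 6.1 must be reconciled on whether a child off dupilumab is still due for the week 24 challenge, so that the reason for a missing challenge can be recorded consistently.

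The cost is one sentence in each of two SAP sections, two consistency edits and one extra table, plus the protocol clarification. The estimate may be slightly lower and mildly conservative: about 0.3 points too low per affected child if off-drug children pass at 8%.

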8.7. Concomitant Medications and Procedures

Any treatment administered from the time of the first dose of study drug to the final study visit will be considered concomitant medication. This includes medications that were started before the study and are ongoing during the study.

The use of prohibited medications should only be considered when necessary for the patient's care and well-being and when there are no other options. Their use results in permanent treatment discontinuation but not discontinuation from study.

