8.7.1. Prohibited Medications and Procedures

Treatment with the following concomitant medications is prohibited during the study:

- Treatment with a live (attenuated) vaccine; below is a list of examples of such vaccines. Refer to study manual for a current, comprehensive list of prohibited vaccines

Chickenpox (Varicella)	Oral typhoid
FluMist-Influenza	Rubella
Intranasal influenza	Smallpox (Vaccinia)
Measles (Rubeola)	Yellow fever
Measles-mumps-rubella combination	Bacillus Calmette-Guerin
Measles-mumps-rubella-varicella combination	Rotavirus
Mumps	Varicella Zoster (shingles)
Oral polio (Sabin)	

- Treatment with an investigational drug (other than dupilumab)
- Treatment with immunomodulating biologic agents, including anti-IgE
- Treatment with allergen immunotherapy
- Treatment with systemic (oral, IV, IM, SC) corticosteroids for a duration of more than 5 continuous days, more than 15 days in total, or within 2 days prior to DBPCFCs
- Treatment with any agents known or likely to interact with epinephrine (eg, beta blockers, ACE-inhibitors, tri-cyclic antidepressants, or other drugs)
- Treatment with antihistamines within 5 days prior to screening and within 5 days prior to SPTs and day 1 of DBPCFCs

The following concomitant procedures are prohibited during study participation:

- Major elective surgical procedures

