2.2. Statistical Hypothesis

The statistical hypothesis is on the primary endpoint, the proportion of patients who achieve a cumulative dose of at least 444 mg peanut protein during a DBPCFC at week 24.

Let μ_D be the true proportion of patients who achieve a cumulative dose of 444 mg peanut protein during a DBPCFC at week 24 for dupilumab. The following hypothesis will be tested at the 2-sided 5% significance level:

Null hypothesis H_0 : $\mu_D = 8\%$, ie, the proportion of patients who achieve a cumulative dose of 444 mg peanut protein during a DBPCFC at week 24 is 8% (Vickery, 2018).

Alternative hypothesis H_a : $\mu_D \neq 8\%$, ie, the proportion of patients who achieve a cumulative dose of 444 mg peanut protein during a DBPCFC at week 24 is different from 8%.

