2.3. Sample Size and Power Considerations

The sample size is determined to adequately power the primary endpoint of the proportion of patients who pass at least a DBPCFC of 444 mg (cumulative) of peanut protein at week 24. Based on assessment of clinical data from Aimmune Therapeutics AR101 phase 3 peanut OIT study (ARC003), it is assumed that the rate of a tolerated cumulative dose of at least 444 mg of peanut protein on DBPCFC at week 24 is 8% in placebo (Vickery, 2018) and 29% in dupilumab.

A sample size of 20 patients will have 80% power to detect the 21% difference in tolerated rate at the 2-sided 5% significance level. Allowing for a dropout rate of around 15%, approximately 24 patients will be required. The sample size calculations were done by one-sample Chi-square test (normal approximation) using nQuery + nTerim 4.

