4.4. Rescue Medication/or Prohibited Medication During Study

Prohibited concomitant medications/procedures

Treatment with the following concomitant medications is prohibited during the study:

• Treatment with a live (attenuated) vaccine (see protocol Section 8.7.1 for the list of vaccine)

Protocol: R668-ALG-1702

Date: March 3, 2021

- Treatment with any agents known or likely to interact with epinephrine (e.g., beta blockers, ACE-inhibitors, tri-cyclic antidepressants, or other drugs)
- Treatment with antihistamines within 5 days prior to screening and within 5 days prior to SPTs and day 1 of DBPCFCs

The following concomitant procedures are prohibited during study participation:

• Major elective surgical procedures

Rescue Treatment (including both medications and procedures)

The following concomitant treatments will require permanent study drug discontinuation:

- Treatment with an investigational drug (other than dupilumab)
- Treatment with immunodulating biologic agents, including anti-IgE
- Treatment with allergen immunotherapy
- Treatment with systemic (oral, IV, IM, SC) corticosteroids for a duration of more than 5 continuous days, more than 15 days in total, or within 2 days prior to DBPCFCs

The following concomitant treatments of allergic reactions will NOT require permanent study drug discontinuation:

- IM or SC administration of epinephrine
- Oral antihistamines
- Short acting inhaled bronchodilators
- Inhaled corticosteriods
- Systemic (oral, IV, IM, SC) corticosteroids for a duration of less than 5 continuous days, less than 15 days in total, and at least 2 days prior to DBPCFCs

Treatment of acute-allergic reactions will be categorized as follow,

- Screening DBPCFC of peanut protein
- Week 24 DBPCFC of peanut protein
- Week 36 DBPCFC of peanut protein

Blinded adjudication of rescue treatments will be implemented before database locks by considering the type of medication or procedure, indication, timing, frequency and the potential impact of the use of the prohibited medication or procedure. The rescue treatments will be adjudicated by the clinical study director and the adjudication procedure will be documented.

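### The SAP adjudicates rescue and prohibited treatments but gives the result no role in any efficacy analysis, and the protocol leaves open whether such patients are challenged at week 24

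*SAP*

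**What the plan says.** **Treatments and adjudication.** SAP 4.4 introduces one list with the words "The following concomitant treatments will require permanent study drug discontinuation". It names other investigational drugs, immunomodulating biologics including anti-IgE, allergen immunotherapy, and systemic corticosteroids. For steroids, protocol 8.7.1 sets the limits as more than 5 continuous days, "more than 15 days in total, or within 2 days prior to DBPCFCs". SAP 4.4 then states: "Blinded adjudication of rescue treatments will be implemented before database locks by considering the type of medication or procedure, indication, timing, frequency", together with the potential impact of the prohibited treatment. Both documents also prohibit antihistamines in the 5 days before the first day of a DBPCFC, but SAP 4.4 leaves them out of the discontinuation list.

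**Efficacy rules.** SAP 4.5.1 defines a pass by the challenge reaction alone. For a missing week 24 challenge, SAP 5.6.1 uses multiple imputation if COVID-19 was the reason. Otherwise: "If a patient does not have available DBPCFC data at week 24 due to reasons not related to COVID-19, the patient will be considered as" (the status given is non-responder). SAP 5.6.2 applies the same logic to the 1044 and 2044 mg endpoints and substitutes the screening value for the log-dose change. The supportive analysis takes every patient with an available week 24 peanut challenge. SAP 10.1 and protocol 11.4.3.1 add nothing on other treatment.

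**Who is challenged.** On prohibited medication, protocol 8.7 says: "Their use results in permanent treatment discontinuation but not discontinuation from study". Protocol 8.3.2 asks patients who stop study drug but stay in the study to attend all remaining visits. Protocol 8.3.2.1 lists any prohibited medication among its reasons. Its heading refers to stopping both dupilumab and the food challenge, but the sentence below it stops only study drug dosing.

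**The concern.** Some of the listed treatments could raise the dose of peanut protein a patient tolerates, or mask a reaction. The plan's own wording on potential impact recognises this. An adjudication of impact that feeds no efficacy rule is unfinished: a patient judged to have taken such a treatment and then observed to pass 444 mg is counted exactly like any other responder.

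The trial has one arm and is read against a fixed 8% reference. No control group is exposed to the same concomitant treatment, so a pass owed to another therapy would be read as a dupilumab response. The one supportive analysis drops only patients without a challenge, so it keeps these passes as well.

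Steroids shortly before the week 24 challenge are the clearest case. The last study drug dose is at week 22, so stopping study drug dosing, which is all the text of 8.3.2.1 provides, changes nothing for that patient.

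**Working it through.** **1. The plan's own figure.** SAP 2.3 states: "A sample size of 20 patients will have 80% power to detect the 21% difference in tolerated rate at the 2-sided 5% significance level". Inputs are p0 = 0.08, p1 = 0.29, z = 1.960 and 0.842.

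- n = [(1.960·√(0.08·0.92) + 0.842·√(0.29·0.71)) / 0.21]² = [(0.532 + 0.382) / 0.21]² = 18.9, rounded up to 19.
- Power at n = 20 is 81.5%.
- 20 / 0.85 = 23.5, rounded up to 24 enrolled.

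The sample size reproduces and is not at issue.

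**2. Tracing a patient through the text.** Take a patient who received prohibited treatment before week 24.

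- If the challenge is withheld, the result is missing for a reason unrelated to COVID-19. SAP 5.6.1 makes the patient a non-responder and SAP 5.6.2 assigns the screening value.
- If the challenge is performed and passed, the patient is a responder in the primary analysis (SAP 4.5.1 and 5.6.1) and in the supportive analysis. The adjudication result enters neither.

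The same treatment history thus leads to opposite outcomes, depending on how protocol 8.3.2.1 is read against 8.3.2 and 8.7.

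**3. Where the treatment would appear.** SAP 5.3 gives medication tables, a Kaplan-Meier curve of time to first rescue treatment, and a medication listing with indication and study day. SAP 5.4 gives listings of protocol deviations and of discontinuations with reasons. None of these is an efficacy analysis.

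**4. Size at N = 24.** One reclassified pass is 1/24 = 4.2 points and two are 2/24 = 8.3 points. Clopper-Pearson limits are the 2.5% quantile of Beta(k, n−k+1) and the 97.5% quantile of Beta(k+1, n−k):

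- 4/24 = 16.7% (4.7 to 37.4)
- 5/24 = 20.8% (7.1 to 42.2)
- 6/24 = 25.0% (9.8 to 46.7)
- 7/24 = 29.2% (12.6 to 51.1)

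The design assumption of 29% corresponds to 0.29 × 24 ≈ 7 passes.

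**5. A worst-case illustration.** Suppose m patients pass solely because of another therapy and the rest have a true pass rate of 8%. The expected observed rate is (m + (24 − m)·0.08)/24, which is 8.0%, 11.8% and 15.7% for m = 0, 1 and 2. The value of m is an assumption; the documents give no frequency of such use.

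**The case against.** **The challenge may not happen.** If the heading of protocol 8.3.2.1 governs, the food challenge stops along with dupilumab and the missing-data rule already gives non-response. The individual stopping rules in protocol 6.1.3.1 are also headed as covering both study drug and challenge. This objection stands in part: a reader might infer that such patients are certain to be challenged and counted, and the documents do not settle that. They do not settle the opposite either. The text of 8.3.2.1 stops only dosing, 8.3.2 and 8.7 keep the patient on the visit schedule, and use discovered after a completed challenge is not addressed.

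**The cases are traceable.** A reader might infer that the treatment would go unseen. It would not: the SAP 5.3 and 5.4 listings would show it, and about 24 patients can be read line by line. What is missing is an efficacy result that takes it into account.

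**Not every such pass is false.** A patient dosed through week 22 who then takes a steroid might have passed on dupilumab alone. Automatic non-response can therefore bias the rate downward. Counting observed outcomes whatever else was taken is a legitimate strategy. Neither document declares it, however, and a planned adjudication of impact sits oddly with it.

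**No success criterion is set.** One could infer that a single patient decides the trial, because the lower limit crosses 8% between 5/24 and 6/24. SAP 1.2.3 makes the analysis descriptive and removes the p-value. SAP 2.2 keeps the hypothesis wording, but no rule ties success to the lower limit.

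**Conclusion.** The gap is real and modest. The SAP plans an adjudication and then gives it no role in SAP 5.6.1, 5.6.2 or 10.1, so an observed week 24 pass after anti-IgE, allergen immunotherapy or prohibited systemic corticosteroid counts as a response in both planned analyses. Whether such a pass can arise depends on protocol passages that conflict and must be reconciled.

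The distortion is at most 4.2 points per patient at N = 24, and less to the extent that the patient would have passed anyway. Assuming 0 to 2 such patients, it lies between 0 and 8.3 points, and zero is possible. The interval shift from 7.1% to 9.8% at the lower limit, against the 8% reference, illustrates sensitivity only. The documents do not support a claim that the result is biased, that every such pass is caused by the other therapy, or that one patient determines success.

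**What to change.** 1. Reconcile protocol 8.3.2, 8.3.2.1 and 8.7 on whether the week 24 challenge takes place after prohibited treatment. Align the SAP 4.4 discontinuation list with protocol 8.3.2.1 and 8.7, which attach discontinuation to any prohibited medication. Which clinical rule should apply is for the sponsor.
2. Add to SAP 5.6.1 and 5.6.2, and enter in SAP 10.1, a pre-specified analysis for any patient adjudicated before database lock as having received, before the week 24 peanut challenge, a prohibited treatment that could affect it. That patient is a non-responder at 444, 1044 and 2044 mg and takes the screening value for the log-dose change. This can be the primary rule. If the sponsor prefers to count observed passes, state that choice and run this as a sensitivity analysis.
3. Extend the adjudication and this analysis explicitly to antihistamines within 5 days before the challenge as well as the SAP 4.4 discontinuation list. Otherwise a pass after antihistamine use remains uncovered.

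The cost is a few lines of SAP text and one additional table, using an adjudication already planned. The pass rate may come out slightly lower, and possibly conservative. Writing the rule before lock also avoids an ad hoc decision in an open-label trial whose data the sponsors may review internally (SAP 7).
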